## 4.2 Data processing

The SHUEE uses a numerical scoring system. The participants performance is analysed and scored using the Spontaneous Functional Analysis (SFA), the Dynamic Positional Analysis (DPA), and the Grasp/Release Analysis (GRA).

## Spontaneous Functional Analysis (SFA):

In order to assess the participant's actual function of the affected extremity, a spontaneous use score is recorded. For this portion of the scoring, a modified House

scale is used. The scale is shown in the table below. The SFA is recorded each of the 9 tasks.

Modified House Scale			
Class	Designation	Activity level	
0	Does not use	Extremity not utilised in any capacity for	
		completion of task.	
1	Poor passive assist	Uses as stabilising weight only.	
2	Passive assist	Can hold onto object paced in hand; may	
		stabilise the object for use by other hand.	
3	Poor active assist	Can actively grasp object and stabilise	
		object for use by other hand.	
	Active assist	Can actively grasp and stabilise object for	
4		use by other hand; may manipulate object	
		with affect hand.	
5	Spontaneous use,	Performs bimanual activities easily; may	
	partial to complete	use the hands spontaneously or without	
		reference to the other hand.	

## Dynamic Positional Analysis (DPA):

The dynamic positional analysis score for each of the tasks is related to joint and limb segment movement. The DPA documents the dynamic, segmental alignment of the extremity when performing the task. The DPA assesses the following five functional/anatomical segments:

Thumb segment alignment:

- Thumb in palm Any combination of metacarpophalangeal joint (MCP) flexion or interphalangeal joint (IP) flexion resulting in the thumb being placed beneath the fingers, in the palm. No visible web space is seen, from any angle at the first web space.
- Thumb Web Space Closed No visible space at the first web space. Thumb is adducted and may have a hyperextended IP joint, but does not cross index metacarpal into palm. No visible web space is seen, from any angle at the first web space.
- Thumb Web Space Open Thumb MCP in abduction. Any visible web space constitutes an "open" score. Participant able to extend or abduct thumb to grasp object. Participant does not have to maintain abducted posture to be given this score.

Finger Segment Alignment

Fingers are graded as a group because they frequently move in composite flexion or extension. The tasks used for thumb evaluation are used for finger evaluation.

- Flexion MCP maintained in greater than 45° flexion. Fingers are held in palm, in variable flexion pattern at DIP joints.
- Neutral Fingers are held in midrange with adequate alignment for task. Fingers easily fluctuate between flexion and extension patterns with no joint aberrations.
- Extension Fingers are held in hyperextension at MCP or IP joints. Associated swan neck deformities or extensor splaying may also be present.

Wrist Segment Alignment

- Flexion Wrist is held in flexed position throughout task; with or without ulnar deviation; any measurement between 0° 80° of flexion.
- Anatomical neutral Wrist in anatomical neutral position of 0° for all or portion of task; with or without ulnar deviation.
- Extension Wrist extends past anatomical neutral position for all or portion of the task; any measurement between 0° 70° of extension.
- Ulnar deviation Wrist is held in an ulnarly deviated position throughout task; any measurement between 0° 30°.
- Neutral Wrist is in the neutral plane; within 5° of neutral.
- Radial deviation Wrist is held in a radial deviated position throughout task; any measurement between 0° - 20°

Forearm Segment Alignment

- Extreme pronation Excessive pronation, no active supination, resulting in palm away from body; any measurement 91° or greater.
- Pronation Pronated at rest with no active supination during task, resulting in palm to floor; any measurement 0° 90°.
- Neutral Active movement from pronated position to neutral, resulting in 0° palm towards body.
- Supination Active movement beyond neutral to supination with palm open to face. Anything 0° 90°.

Elbow Segment Alignment

- Extreme flexion Participant is unable to actively extend past 90°.
- Flexion Participant is unable to extend past 30°.
- Extension Participant is able to extend between 30° and 0°.

## Grasp and Release Analysis (GRA):

The GRA documents if the participant can or cannot grasp and release the object with the wrist in the three different positions. A yes (Y) or no (N) for grasp and release is provided contingent on the participants ability to close and open fingers with the wrist

maintained in each position. Video examples of optimal grasp and release for each position are available online.

The SWE images obtained will be processed using a custom software developed in MATLAB (The MathWorks, Natick, MA, USA) to process the images semiautomatically.

The EMG signals obtained will be processed using a custom software developed in MATLAB that will ensure the signal is low-pass filtered for noise, full wave rectified and smoothed.

## 4.3 Equipment

A camera will be used to video record for future data processing.

For the SHUEE activity, the following will be used to obtain the corresponding SHUEE scores:

- Billfold style wallet to hold paper money
- 8 x 10 sheet of standard weight paper
- Three American dollar sized bills made of standard weight paper
- Four plastic coins of any size
- One wide-mouth clear 2-2 /2" diameter bottle with 2-2 /2" screw cap
- One Play-Doh® can
- Stickers of any size or type One 30" ball

For the ultrasound measurements, the following devices will be used:

- LOGIQ E10 Ultrasound R2 system (GE Healthcare, Chicago, IL, USA)
- A ML6-15-D probe (GE Healthcare, Chicago, IL, USA)
- Ultrasound gel

The equipment required for the tremor tests includes two triaxial accelerometer sensors (Delsys Trigno).

- Trigno wireless EMG system (Delsys, Natick, MA, USA)
- LOGIQ E10 Ultrasound R2 system (GE Healthcare, Chicago, IL, USA)
- A ML6-15-D probe (GE Healthcare, Chicago, IL, USA)
- Ultrasound gel

## 4.4 Outcome measures

Primary outcome measure: The primary outcome measures are the elasticity of the tendons and the anthropometrics of the muscles before and after BTX-A injections.

Secondary outcome measure: The secondary outcome measure is the comparison of computational models for data collected before and after BTX-A injections.

# 5. Adverse Events

## 5.1 In the event of an irritation due to ultrasound gel or EMG sensor adhesive

Participants will be informed that if they notice any irritation due to the contact with the ultrasound gel or EMG sensor adhesive during or immediately following the study, they should inform the investigators. The area will be cleaned with soap and water. Participants will be informed that if the irritation persists for more than 24 hours, they should inform the investigators of this study so that we may advise them as to whether to consult their local medical clinic.

## 5.2 In the event of fatigue during the test procedure

As some physical tasks will be undertaken, the participant may suffer from fatigue. If this happens, the participant should inform the investigators and the tests will stop until the participant feels prepared to continue with the test procedure.

#### 5.3 Reporting of non-serious adverse events and serious adverse events

If any injuries, illnesses, or accidents should occur, a clinician will be called and all accidents and near misses will be reported.

All adverse events should be reported. Depending on the nature of the event the reporting procedures below should be followed. Any questions concerning adverse event reporting should be directed to the Chief Investigator in the first instance.

#### 5.3.1 Non serious adverse events

All such events, whether expected or not, should be recorded- it should be specified if only some non-serious AEs will be recorded, any reporting should be consistent with the purpose of the trial end points.

#### 5.3.2 Serious adverse events

An SAE form should be completed and emailed to the Chief Investigator within 24 hours. However, relapse and death due to pre-existing condition, and hospitalisations for elective treatment of a pre-existing condition do not need reporting as SAEs.

All SAEs should be reported to the NHS REC where in the opinion of the Chief Investigator, the event was:

- 'related', ie resulted from the administration of any of the research procedures; and
- 'unexpected', ie an event that is not listed in the protocol as an expected occurrence

Reports of related and unexpected SAEs should be submitted within 15 days of the Chief Investigator becoming aware of the event, using the NRES SAE form for non-IMP studies. The Chief Investigator must also notify the Sponsor of all related and unexpected SAEs.

Local investigators should report any SAEs as required by their Local Research Ethics Committee, Sponsor and/or Research & Development Office Contact details for reporting SAEs [contact] CI email (and contact details below) [contact] [name] Please send SAE forms to: [contact] [contact] (Mon to Fri 09.00 – 17.00)

## 6 Assessment and follow up

All ultrasound scans will be reported to and reviewed by the clinical care team so that in the event of incidental findings these can be appropriately investigated and acted upon.\_There will be no routine follow up for participants. The end of study is defined as the end of the third data collection session or the final data collection session for that participant.

The end of study is defined as the end of the third data collection session or the final data collection session for that participant.

# 7. Statistics and data analysis

The sample size has been calculated using a power analysis calculation. The data will be analysed using Shapiro-Wilk test to test for normality. Depending on the results of the Shapiro-Wilk test, the data will be further analysed using t-tests and ANOVA tests for comparison of data.

Data and all appropriate documentation will be stored for a minimum of 10 years after the completion of the study, including the follow-up period.

# 8 Regulatory Issues

## 8.1 Ethical Approval

The Study Coordination Centre has obtained approval from the NHS Research Ethics Committee (REC) and Health Regulator Authority (HRA). The study must also receive confirmation of capacity and capability from each participating NHS Trust before accepting participants into the study or any research activity is carried out. The study will be conducted in accordance with the recommendations for physicians involved in research on human subjects adopted by the 18th World Medical Assembly, Helsinki 1964 and later revisions.

#### 8.2 Consent

Consent to enter the study must be sought from each participant only after a full explanation has been given, an information leaflet offered and time allowed for

consideration. Signed participant consent should be obtained. The right of the participant to refuse to participate without giving reasons must be respected. After the participant has entered the study the clinician remains free to give alternative treatment to that specified in the protocol at any stage if he/she feels it is in the participant's best interest, but the reasons for doing so should be recorded. In these cases the participants remain within the study for the purposes of follow-up and data analysis. All participants are free to withdraw at any time from the protocol treatment without giving reasons and without prejudicing further treatment.

The parent/carer will be required to complete and sign the consent form prior to their child's participation in the study. If the participant is over the age of 16 years of age, they will be asked to sign a consent form. For participants who are 15 and turn 16 whilst on the study, they will also be asked to sign a consent form. For participants under the age of 16, they will sign an assent form.

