# 1. Introduction

Cerebral palsy (CP) occurs in 2 to 3.5 of 1000 live births, with spastic CP, accounting for the majority of cases (1,2). This is a specific form of hypertonia that leads to an imbalance of muscle forces, which presents in the abnormal position of the limb. These abnormal positions can interfere with various motions of the upper limb, such as grasp-to-release function and the tasks involved in activities of daily living (ADLs) (3).

Tendon transfer is a popular surgical option to correct these deformities, whilst botulinum toxin type A (BTX-A) is a common non-surgical option and can be used to delay surgery and reduce spasticity. Repeat injections are considered where the clinical effects have diminished, and new goals have been established.

BTX-A has been reported as a safe and effective treatment with the ability to enhance performance in school activities, ADLs (4) and functional movement (5), particularly in children with mild movement impairments (6). There was an observation of increased muscle volume in the non-injected muscle and decreased volume in the injected muscle following BTX-A treatment in a population of children with spastic CP (7). Additionally, it has been found that BTX-A can induce muscle weakness in the target and non-target muscles (8,9), but there is little knowledge of how the mechanical properties of muscles contribute to this induced muscle weakness. Where a patient may require a tendon transfer surgery, following BTX-A treatment, the properties of the involved tendons may affect the outcome of surgery, due to the contribution of tendon mechanical properties to force generation of the muscle-tendon unit (10). This raises the questions of how BTX-A induced adaptations affect the functional ability of the upper extremity and how these adaptations may affect length of treatment. Addressing these questions will give us an indication of when decisions should be made to continue BTX-A treatment or to begin to consider surgery. Moreover, it is important to know if the continuous use of BTX-A affects the performance of the associated tendon in future surgical intervention. Currently, no objective evaluation is done to assess muscle and tendon mechanical properties prior to surgical intervention.

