## 3.2 Exclusion Criteria

- 1. Any surgical intervention on the upper extremity in the last 6 months.
- 2. Any known allergy to adhesives.

- 3. Any known skin allergies.
- 4. Unable to obtain informed consent from participant's parent/carer.
- 5. The participant and the participants parent/carer are not able to speak, read and understand English.

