## 3.4 Sample size

Sample size: 8 healthy participants between the ages of 4 and 18.

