# 4. Study Design

## 4.1 Methodology

Participants will be asked to take part in all the tests listed below. This will take approximately 1 hour in total. The participants will attend three sessions at the 1st Floor, Paediatric Outpatients, Chelsea and Westminster Hospital ([name]). The first session being before they start BTX-A treatment, the second session will be between 3 weeks and 6 months after treatment and the third session will be at least 6 months after treatment. All the sessions will consist of the procedures described in sections 4.1.1, 4.1.2 and 4.1.3.

Upon arrival at the 1st Floor, Paediatric Outpatients Department, participants' carers will be asked to review the participant information sheet and sign the consent form, if they have not already done so. If the participant is over the age of 16 years of age, they will be asked to sign a consent form. For participants under the age of 16, they will sign an assent form. Demographic information regarding the participant's age (current year and month), diagnosis and any significant birth history or previous surgery will be documented. Participants must consent to the clinical care team

reviewing the ultrasound scan reports to ensure any incidental findings can be appropriately investigated and acted upon.

A camera with a tripod, will be used to video record future data processing. The participant will be seated at a table and the camera will be focused on the participant's upper extremity and the tabletop. For the best observation of participant's extremity, long hair will be restrained, if possible, and their sleeves will be rolled up above the elbow. The participant will be positioned sideways to the camera with uninvolved side closest to the camera and the involved side furthest from the camera. This position allows best visibility of the involved hand and thumb for the video.

Participants will be asked to take part in a series of three main activities: Shriners hospital upper extremity evaluation, ultrasound measurements and EMG measurements. Following each task, a 3-minute rest period will be designated in order to avoid the effects of fatigue.

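### Section 8.2 keeps children who receive other treatment in the data analysis, so readings taken after surgery, or without any injection, could enter the after-BTX-A comparison

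*Protocol*

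**What the plan says.** Protocol section 8.2 (Consent) states that after entry "the clinician remains free to give alternative treatment to that specified in the protocol at any stage", with the reasons to be recorded. The next sentence reads: "In these cases the participants remain within the study for the purposes of follow-up and data analysis".

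The comparison that these children would stay in is set out in section 4.4: "The primary outcome measures are the elasticity of the tendons and the anthropometrics of the muscles before and after BTX-A injections". Section 2.1 states the aim as the effect of BTX-A at several times after injection. No control group is described.

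On timing, section 4.1 places session 1 before treatment starts and adds that "the second session will be between 3 weeks and 6 months after treatment and the third session will be at least 6 months after treatment". Section 7 names a normality test followed by t-tests and ANOVA. It draws no distinction for readings taken after another treatment.

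Surgery is restricted only at entry, in section 3.2: "Any surgical intervention on the upper extremity in the last 6 months". The Introduction discusses tendon transfer as a surgical option that may follow BTX-A, and says of further toxin: "Repeat injections are considered where the clinical effects have diminished, and new goals have been established".

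**The concern.** Keeping everyone in the analysis whatever treatment they later receive has a clear purpose in a randomised trial, where it protects the comparison between arms. Here there is no such comparison. The quantity of interest is what BTX-A does to particular muscles and their tendons, estimated from each child's own change.

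Two kinds of reading do not measure that quantity:

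- **Readings after upper-limb surgery or other replacement treatment.** Section 4.1.2 measures the origin and insertion tendons of the injected muscles. Surgery may alter these tendons directly.
- **Readings from a child who was never injected.** Consent and session 1 come before the injection, and treatment may change at any stage. A child who is enrolled and then treated otherwise stays in the analysis under section 8.2, although the later sessions do not follow BTX-A at all.

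With 8 children, each one carries an eighth of the mean. A longer-term estimate that mixes toxin effects with the effects of surgery would be hard to interpret. It would also be passed on to the computational models that the secondary objective relies on.

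**Working it through.** **1. The plan's own figure.** Section 3.4 gives "Sample size: 8 healthy participants between the ages of 4 and 18", and section 7 says "The sample size has been calculated using a power analysis calculation". No alpha, sidedness, power, effect size or SD is stated, so the 8 cannot be reproduced. As a yardstick I solved a paired t-test (noncentral t, 7 degrees of freedom) for the standardised within-child change that n = 8 can detect. All settings are assumptions.

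| Test at 5% | 80% power | 90% power |
|---|---|---|
| Two-sided | 1.16 SD | 1.34 SD |
| One-sided | 0.98 SD | 1.15 SD |

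**2. Shift in the mean change.** Let k of the 8 children be affected, and let the other treatment move each one's change by c, in SDs of the within-child change. If μ is the true mean change after BTX-A alone, then

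expected mean = [(8 − k)μ + k(μ + c)] / 8 = μ + kc/8.

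The documents give neither k nor c, so a range is shown.

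| k | c = 1 SD | c = 2 SD |
|---|---|---|
| 1 | 1/8 = 0.125 SD | 2/8 = 0.25 SD |
| 2 | 2/8 = 0.25 SD | 4/8 = 0.50 SD |
| 3 | 3/8 = 0.375 SD | 6/8 = 0.75 SD |

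Against the 1.16 SD yardstick, one affected child accounts for 0.125/1.16 = 11% to 0.25/1.16 = 22%. Two account for 22% to 0.50/1.16 = 43%.

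**3. Never-injected child.** If such a child has no change on average (an assumption), then c = −μ and the expected mean becomes μ(8 − k)/8. One child dilutes the estimate to 7/8 = 87.5% of its true size, and two dilute it to 6/8 = 75%.

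**4. Effect on the test.** In a simulation of 200,000 runs with no BTX-A effect, a nominal two-sided 5% paired t-test rejected as follows.

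| k | c = 1 SD | c = 2 SD |
|---|---|---|
| 1 | 4.9% | 4.5% |
| 2 | 6.9% | 8.4% |
| 3 | 10.5% | 17.6% |

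With one affected child the false-positive rate hardly moves, because the outlying value also inflates the SD. The main harm is a biased estimate. Excess false positives become appreciable only with two or three affected children.

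**5. Price of leaving readings out.** On the same yardstick (two-sided 5%, 80% power), the detectable change is 1.16 SD at n = 8, 1.27 at n = 7, 1.44 at n = 6 and 1.68 at n = 5.

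**The case against.** The sentence in section 8.2 sits under Consent and says who stays in, not how their later readings are classed. Retaining children after a change of treatment is ordinary practice. A statistical analysis plan, if there is one, is not at hand and may set the rule. A reader might infer that readings after surgery or re-injection *will* be counted as the BTX-A effect, but the documents do not say so. What they support is that such readings *could* be. The point still stands, because section 8.2 names data analysis explicitly and is the protocol's only statement on the matter. An analysis plan that set these readings apart would have to qualify it.

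A reader might also extend the criticism to re-injection. The rule concerns treatment other than the one the protocol specifies, and a further injection is more BTX-A. The objectives speak of injections in the plural, and the Introduction is interested in continued use. Readings after re-injection may therefore belong to the study question. By the Introduction's account, re-injection is considered once the effect has worn off, so dropping those readings could select children whose response lasted. This part of the objection stands.

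Two further inferences go too far. The Introduction presents surgery and repeat injections as possibilities and gives no rates, so they cannot be called the expected next steps. Session 3 is the most plausible place for them only because more time has passed. And section 3.2 excludes recent surgery only, so it does not show that the protocol regards every operated limb as unfit for analysis.

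Finally, summarising outcomes whatever treatment followed is a legitimate choice even in a single group. It answers a different question from the effect of BTX-A on the tissue, which is why it suits a sensitivity analysis here.

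**Conclusion.** The concern holds in a limited form. Section 8.2 fixes a rule that does not fit an uncontrolled before/after study of injected muscles and their tendons, and no other section sets apart readings taken after surgery, after other replacement treatment, or without any injection. The documents do not establish that such readings will be misclassified, how often the events occur, or that re-injection falls under the rule.

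The size is conditional. It rests on an assumed 1 to 2 SD difference in affected children and an assumed one or two such children out of 8, which gives a shift of 0.125 to 0.50 SD in the mean change. If no child changes treatment, there is no effect. The correction is worth making because so few children carry the estimate and because it is cheap.

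**What to change.** Leave the clinician's freedom and the follow-up of these children as they are, and amend the analysis part of the rule in section 8.2, or add to section 7, for example:

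*Children whose treatment changes stay in follow-up. The primary before/after comparison uses readings taken after the study injection and before any upper-limb surgery or other replacement treatment of the studied limb. A sensitivity analysis includes all readings. Readings after a further BTX-A injection are flagged and reported by number of injections received.*

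At sessions 2 and 3, record the date and type of every intervening treatment of the limb, including further BTX-A. Section 8.2 currently asks only for the reasons.

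The cost is a short amendment and one field on the session form, with no change to patient care. A few session-3 values may leave the primary analysis. With 8 children that is a real loss of precision, as step 5 of the working shows, and the sensitivity analysis lets the reader see what those values would have done.
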